**Table 2: Management of immune- mediated adverse events**

Immune-related AEs are specific to immunotherapies and vary by organ system. The following immune-related AEs are important identified risks for M7824:
 
 
• Immune-related pneumonitis
 
• Immune-related hepatitis
 
• Immune-related colitis
 
• Immune-related nephritis and renal dysfunction
 
• Immune-related endocrinopathies
 
• (thyroid disorders, adrenal insufficiency, type 1 diabetes mellitus, pituitary disorders)
 
• Immune related rash
 
• Other immune-related events (myositis, myocarditis, encephalitis)
 
 
The following immune-related AEs are important potential risks for M7824:
 
 
• Guillain-Barré syndrome
 
• Uveitis
 
• Pancreatitis
 
• Myasthenia gravis/myasthenic syndrome
 
 
Recommended guidance and management for specific irAEs are provided in the current National Comprehensive Cancer Network (NCCN) guideline available at http://www.nccn.org.
 
Requirements in addition to NCCN guidelines:
 
 
• Permanent treatment discontinuation is required in case of immune-related Grade 4 rash/inflammatory dermatitis, nephritis, autoimmune hemolytic anemia, hemolytic uremic
 

--

syndrome, aplastic anemia, immune thrombocytopenia, acquired thrombotic thrombocytopenic purpura inflammatory arthritis, myositis and polymyalgia-like syndrome.

- For Grade 4 immune-related lymphopenia, permanent treatment discontinuation will be required, if lymphopenia is considered immune-related in nature, no clear alternative explanation exists for the event, and it does not resolve within 14 days. Permanent treatment discontinuation is not required when the AE is manifested by a single laboratory value out of normal range without any clinical correlates. In this case, treatment should be held until the etiology is determined. If the event is not considered immune-related and resolves to Grade  $\leq 1$ , restarting treatment may be considered.
- For Grade 1 immune-related pneumonitis: continue treatment. If clinically indicated, monitor participants weekly or more frequently as needed with history, physical examination and pulse oximetry. If symptoms appear and/or changes in the physical exam are noted, treat as Grade 2.
- For myositis: in case of management with rituximab, treatment should be discontinued.
- For Grade 3 or 4 endocrinopathies: withhold until clinically stable or permanently discontinue depending on severity.
- For hepatitis with no tumor involvement of the liver: withhold if total bilirubin increases to more than 1.5 and up to 3 times ULN, permanently discontinue if more than 3 times ULN
- Hepatitis with tumor involvement of the liver: permanently discontinue if total bilirubin increases to more than 3 times ULN.

### 3.3.1.5 Additional Modifications for Subjects with Grade 2 Infusion-related Reactions

If, in the event of a Grade 2 infusion-related reaction that does not improve or worsens after implementation of the modifications indicated in [Table 1](#).

- Management of immune-mediated reactions is described in [Table 2](#).

**Table 1:** Treatment Modifications for Symptoms of Infusion-related Reactions including Immediate Hypersensitivity

NCI-CTCAE Grade	Treatment Modification

Grade 1 - mild Mild transient reaction; in general, infusion interruption not indicated; intervention not indicated
	
 
• Increase monitoring of vital signs as medically indicated as participants are deemed medically stable by the attending Investigator.
 
• Hold infusion if deemed necessary by the investigator.
 

Grade 2 – moderate Therapy or infusion interruption indicated but responds promptly to symptomatic treatment (for example, antihistamines, nonsteroidal
	
 
• Stop the infusion of the study intervention.
 
• Increase monitoring of vital signs as medically indicated as participants are deemed medically stable by the attending Investigator.
 

anti-inflammatory drugs, narcotics, IV fluids); prophylactic medications indicated for $\leq 24$ h.	
 
• If symptoms resolve quickly, resume infusion at 50% of original rate with close monitoring of any worsening signs and symptoms, otherwise dosing held until resolution of symptoms with mandated premedication for the next scheduled visit.
 
• If not improving, consider administration of glucocorticoids and stop the infusion for that day.
 
• If the participant has a second IRR Grade <math>\geq 2</math> on the slower infusion rate despite premedication, the infusion should be stopped, and the investigator may consider withdrawal of this participant from the study.
 


Grade 3 or Grade 4 – severe or life-threatening
 
 
○ Grade 3: Prolonged (for example, not rapidly responsive to symptomatic medication and/or brief interruption of infusion); recurrence of symptoms following initial improvement; hospitalization indicated for clinical sequelae.
 
○ Grade 4: Life-threatening consequences; urgent intervention indicated.
 
	
 
• Stop the infusion of study intervention immediately and disconnect infusion tubing from the participant with additional appropriate medical measures and closely monitor until deemed medically stable by the attending Investigator. Hospitalization and/or close monitoring is recommended Administration of glucocorticoids may be required
 
• For Grade 3 or 4 IRRs, permanent discontinuation of study intervention is mandated.
 

Once the infusion is interrupted or rate reduced to 50% of previous infusion rate, it must remain decreased for all subsequent infusions. For all types and grades of infusion reactions, details about drug physical constitution, method of preparation, and infusion must be recorded. Participants should be instructed to report any delayed reaction immediately.
	

2 IRR=infusion-related reactions, IV=intravenous, NCI-CTCAE=National Cancer Institute-Common Terminology Criteria for Adverse Event, NSAIDs=nonsteroidal anti-inflammatory drugs.
	

(including reducing the infusion rate by 50%), the investigator may consider treatment with corticosteroids and the infusion of M7824 should be stopped for that day. At the next infusion, the investigator may consider the addition of H2-blocker antihistamines (for example, famotidine), in addition to premedication, for select subjects. However, prophylactic steroids are NOT permitted. If the subject has a second infusion-related reaction Grade  $\geq 2$  on the slower infusion rate, with or without the addition of further medication to premedication, the infusion should be stopped and the subject may be removed from M7824 treatment at the discretion of the investigator.

### 3.3.1.6 Immediate Hypersensitivity Reaction

Hypersensitivity reactions may require immediate intensive care. Bintrafusp alfa should be administered in a setting that allows immediate access to an intensive care unit or equivalent

environment and administration of therapy for anaphylaxis, such as the ability to implement immediate resuscitation measures. Potent steroids (e.g. dexamethasone), catecholamines (e.g. epinephrine), allergy medications (IV antihistamines), bronchodilators, or equivalents and oxygen should be available for immediate access.

A complete guideline for the emergency treatment of anaphylactic reactions according to the Working Group of the Resuscitation Council United Kingdom and can be found at <https://www.resus.org.uk/pages/reaction.pdf>.

### 3.3.1.7 Severe Hypersensitivity Reactions and Flu-like Symptoms

If a hypersensitivity reaction occurs, the subject must be treated according to the best available medical practice including ACLS guidelines.

Subjects should be instructed to report any delayed reactions to the investigator immediately.

#### A. Symptoms

- Impaired airway
- Decreased oxygen saturation (< 92%)
- Confusion
- Lethargy
- Hypotension
- Pale / clammy skin
- Cyanosis

#### B. Management

- Epinephrine injection and IV dexamethasone
- Patient should be placed on cardiac, blood pressure, heart rate, and oxygen saturation monitor immediately
- Alert intensive care unit for possible transfer if required

Treatment is based on clinical assessment and at the discretion of the Investigator. For prophylaxis of flu-like symptoms, a NSAID, for example, ibuprofen 400 mg or comparable NSAID dose, may be administered 2 hours before and 8 hours after the start of each dose of M7824 IV infusion.

### 3.3.1.8 Immune-Related Adverse Events

Immune-related adverse events (irAEs) are specific to immunotherapy. IrAEs are important identified risks for M7824. Immune-related adverse events should be documented as an ‘Adverse Event of Special Interest (AESI),’ and it is recommended to involve the principal investigator at first incidence and subsequently as needed for follow-up. Details of the diagnostic work-up will be requested by the study team. An immune related adverse event (irAE) is defined as off target side effects associated with exposure of immunogenic drug and is consistent with immune mechanism. In the process of identification of irAEs, any possible etiology of neoplastic, infectious, metabolic, toxin, or any other factor should be ruled out. Serologic, histologic (biopsy),

and/or immunologic results should be obtained to evaluate the differential diagnosis and/or support an immune-mediated cause.

The recommendations for irAE management, in accordance with the joint American Society of Clinical Oncology (ASCO) Clinical Practice Guidelines ([Brahmer, 2018](#)) and National Comprehensive Cancer Network ([NCCN Guidelines®](#)). General management by CTCAE v5.0 grading, as per ASCO, is listed below (ASCO organ/system specific toxicity management takes precedent over below general guidelines):

Grade 1: study treatment should be continued with close monitoring, with the exception of some neurologic, hematologic, and cardiac toxicities.

Grade 2: study treatment may be suspended for most Grade 2 toxicities, with consideration of resuming when symptoms revert to Grade 1 or less. Corticosteroids may be administered (initial dose of 0.5 to 1 mg/kg/d of prednisone or equivalent).

Grade 3: study treatment is generally suspended and the high-dose corticosteroids (prednisone 1 to 2 mg/kg/d or methylprednisolone 1 to 2 mg/kg/d) treatment should initiated. Corticosteroids should be tapered over the course of at least 4 to 6 weeks. Some refractory cases may require infliximab or other immunosuppressive therapy.

Grade 4: in general, permanent discontinuation of study treatment is recommended, with the exception of endocrinopathies that have been controlled by hormone replacement.

### 3.3.1.9 Anemia

For anemia events assessed as treatment-related, items queried may include but are not limited to detailed relevant past medical and treatment history, bruising tendency, history of blood transfusions and/or dependency, details such as concomitant medications, all laboratory data, updated dosing information and recent tumor evaluation scans.

M7824 treatment-related anemia is an important risk (see Investigators' Brochure). Notably, there are many reasons for anemia in patients with advanced cancer, and Hb level of at least 9 g/dl is required for this study. A thorough investigation of new anemia cases of unspecified etiology is requested. Safety laboratory testing of relevant blood parameters is conducted per schedule of assessment.

General Guidance for anemia management and evaluation:

- Participants must enter the study with Hgb values at least 9 g/dL and baseline anemia evaluation is conducted per [Table 3](#).
- All relevant hematologic testing for treatment related anemias should be done prior to blood transfusion, if clinically feasible.
- If a participant experiences significant anemia (<8g/dl), then the amount of blood to be drawn may be reduced by not taking blood at selected time points for -exploratory biomarkers. The decision to reduce the time points for these biomarkers will be taken by the investigator in consultation with the medical monitor. This will be documented.
- Transfusion should be performed at the discretion of the investigator, based on clinical assessment and considered when participant experiences significant anemia. Attempt should be made to initiate work-up (as specified below) for cause of anemia prior to transfusion if clinically feasible to not confound this workup.

- Guidance for evaluation of suspected treatment-related anemias is provided in [Table 3](#).

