**Any Grade 3 ADRs require treatment discontinuation except for any of the following:**

- Transient ( $\leq 6$  hours) Grade 3 flu-like symptoms or fever, which is controlled with medical management.
- Transient ( $\leq 24$  hours) Grade 3 fatigue, local reactions, headache, nausea, emesis that resolves to  $\leq$  Grade 1 or Baseline grade.
- Tumor flare phenomenon defined as local pain, irritation, or rash localized at sites of known or suspected tumor that resolves within 7 days with optimal medical management.
- Any single Grade  $\geq 3$  drug-related transaminase, alkaline phosphatase, or bilirubin abnormality with no other associated laboratory (or other) abnormality that is not associated with symptoms or clinical manifestations of hepatitis. If the liver function abnormality not associated with symptoms or clinical manifestations of hepatitis has not resolved to Grade  $\leq 1$  within the subsequent 2 cycles (28 days), the subject should permanently discontinue treatment with M7824.
- Subjects with asymptomatic Grade 3 drug-related amylase or lipase abnormalities may continue treatment.
- .
- Grade 3 Hgb decrease ( $< 8.0$  g/dL) that is clinically manageable with blood transfusions or erythroid growth factor use.
- Increases in Eastern Cooperative Oncology Group performance status (ECOG PS)  $\geq 3$  that resolves to  $\leq 2$  by Day 1 of the next cycle (infusions should not be given if the ECOG PS is  $\geq 3$  on the day of M7824 administration and should be delayed until ECOG PS  $\leq 2$ ).
- Keratoacanthoma and squamous cell carcinoma of the skin. Any suspicious skin lesion should be biopsied for confirmation of diagnosis and be surgically removed as indicated by dermatologist and a dermatological consult obtained.
- Other immune-related ADRs, see NCCN guidelines for the management of immune related adverse events

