**Management of treatment-related anemias is provided in [Table 4](#).**

**Table 3:** Evaluation Guidance of Suspected Treatment-related Anemia AEs

Basic anemia evaluation (prior to transfusion, if feasible)	
CBC with differential (e.g. MCV, RDW, ANC, hemoglobin, hematocrit) Reticulocytes counts Peripheral blood smear for cell morphological assessment Complete metabolic panel including liver panel-LFTs, bilirubin, LDH, renal function, and serum folate, B12 values and other chemistries Coagulation factors (PT, PTT, INR) Urinalysis including culture Iron panel (TIBC, ferritin, Fe) TSH/thyroid panel Fecal-occult blood testing Erythropoietin Haptoglobin	
Further recommendation based on suspected etiology (in addition to baseline anemia testing)	
Unknown etiology, suspect possible hemolysis	Coombs test, fibrinogen, d-dimer Consider hematology consultation. Consider blood transfusion at clinical discretion.
Unknown etiology, suspect possible bleeding	Consider blood transfusion at clinical discretion. Consider surgical/interventional radiology consultation. Consider imaging, as clinically indicated (e.g. FAST scan, CT scan, MRI, angiography). Consider endoscopy (upper/lower)
Unknown etiology despite above work-up	Hematology consultation Consider bone marrow aspiration/morphologic evaluation

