**Table 4: Management of Treatment-Related Anemia**

 
• Hematology assessment must be performed at baseline, prior to each bintrafusp alfa dose, at the end of treatment visit and at 28 (<math>\pm 5</math> days) days post-treatment safety follow-up.
 
• Participants must enter the study with Hgb values at least 9g/dl
 
• All relevant hematological testing for treatment-related anemias should be done prior to a blood transfusion, if clinically feasible
 

Diagnostic Work-up

 
• Baseline Anemia Evaluation               
 
• CBC with emphasis on red cell indices
 
 
 
• If indicated and at clinical discretion, the following should be considered:               
 
• Iron studies
 
• Serum Folate and Vit B12 values
 
• Coagulation factors
 
• Fecal occult blood
 
• Urinalysis
 
• Hormone panel: TSH, Erythropoietin
 
• Peripheral blood smear
 
 
 

Further recommendation based on suspected etiology (in addition to basic anemia testing)

 
• Suspected Hemolysis 
 
• bilirubin, LDH, Coombs test, haptoglobin
 
 
 
• Suspected bleeding: 
 
• Consider imaging/interventional radiology consultation as indicated
 
• Consider imaging and/or endoscopy as clinically indicated
 
 
 
• Suspected aplastic anemia: 
 
• Hematology consultation
 
• Consider bone marrow aspiration/morphologic evaluation
 
 
 

Additional consideration
In general, blood transfusions and erythroid growth factors are permitted as clinically indicated.

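### The Grade 3 hemoglobin exemption does not clearly exclude autoimmune hemolytic anemia, and Tables 3 and 4 give different anemia work-ups

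*Combined protocol and SAP*

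**What the plan says.** **Stopping rules.** In section 3.3.1.2, Grade 3 drug reactions require discontinuation apart from a list of exceptions. One exception is a Grade 3 hemoglobin decrease (below 8.0 g/dL) "that is clinically manageable with blood transfusions or erythroid growth factor use". The last exception on the list refers other immune-related reactions to NCCN guidance. Table 2 requires permanent discontinuation for several Grade 4 immune-related events, autoimmune hemolytic anemia among them, and presents this as an addition to NCCN. Appendix C, Table A8, item 8.1 covers the same diagnosis. At Grade 2 it says to hold and strongly consider a permanent stop. At Grade 3, again hemoglobin below 8.0 g/dL with transfusion indicated, it says to discontinue permanently.

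**Work-up.** Section 3.3.1.9 states: "A thorough investigation of new anemia cases of unspecified etiology is requested". It adds that "Guidance for evaluation of suspected treatment-related anemias is provided in" Table 3, and sends management to Table 4. Table 3's basic list includes "Reticulocytes counts Peripheral blood smear for cell morphological assessment" as well as haptoglobin. Under suspected hemolysis it adds "Coombs test, fibrinogen, d-dimer". Table 4 nevertheless has its own diagnostic section. Its one fixed item is "CBC with emphasis on red cell indices"; the smear and several other tests are left to clinical discretion; and "bilirubin, LDH, Coombs test, haptoglobin" are listed for suspected hemolysis.

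**Baseline.** Section 3.3.1.9 says: "Participants must enter the study with Hgb values at least 9 g/dL and baseline anemia evaluation is conducted per" Table 3. Table 4's baseline entry is the CBC, and footnote 5 of the study calendar (Appendix A) lists routine labs.

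**The concern.** Two safety instructions meet at one hemoglobin level. An investigator reading section 3.3.1.2 finds that a transfusable Grade 3 decrease need not end treatment. An investigator reading Appendix C 8.1 finds that, if the cause is autoimmune hemolysis, it must. Anemia is an adverse event of special interest (section 8.1.6), and patients may enter at 9 g/dL, so a fall of just over 9.0 − 8.0 = 1.0 g/dL reaches the overlap.

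The duplicate work-up bears on whether hemolysis is recognized in the first place. Section 3.3.1.9 asks for work-up to begin before transfusion, where feasible, so that transfusion does not confound it. Someone working from Table 4's list could transfuse without a reticulocyte count, smear or haptoglobin, which are the results that would prompt a Coombs test.

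**Working it through.** No sample size, power or error rate is involved. The check is a comparison of texts and a count of tests.

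**Step 1: do the stopping rules overlap?** Take autoimmune hemolytic anemia with hemoglobin below 8.0 g/dL, manageable with transfusion.

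| Source | What it says for this patient |
|---|---|
| 3.3.1.2, hemoglobin exception | Discontinuation not mandatory; autoimmune hemolysis not excluded |
| 3.3.1.2, last exception | Other immune-related reactions go to NCCN; autoimmune hemolysis not named |
| Table 2 | Permanent stop named at Grade 4, in addition to NCCN; silent on Grade 3 |
| Appendix C 8.1, Grade 3 | Permanently discontinue |

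The threshold is identical in the first and last rows, so one patient can meet both.

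**Step 2: does any text rank them?** Section 3.3.1.8 gives ASCO organ-specific guidance priority, but only over the general Grade 1 to 4 list in that same section. It does not mention 3.3.1.2 or Table 2. The NCCN exception in 3.3.1.2 does not say whether it overrides the hemoglobin exception above it. The order of precedence is therefore unstated.

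**Step 3: how far apart are the work-ups?** Table 3's basic list has 11 groups: CBC; reticulocytes; smear; metabolic panel with LDH, bilirubin, folate and B12; coagulation; urinalysis with culture; iron panel; TSH; fecal occult blood; erythropoietin; haptoglobin. Against calendar footnote 5:

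- covered fully: 3 (CBC, coagulation, TSH)
- covered in part: 2 (chemistry without folate and B12; urinalysis without culture)
- not covered: 6 (reticulocytes, smear, iron panel, fecal occult blood, erythropoietin, haptoglobin)

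3 + 2 + 6 = 11.

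Table 4's treatment of the 6 not covered:

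- discretionary: 4 (smear, iron, fecal occult blood, erythropoietin)
- on suspicion of hemolysis: 1 (haptoglobin)
- not listed: 1 (reticulocytes)

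4 + 1 + 1 = 6.

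Three of the 6 bear on hemolysis: reticulocytes, smear and haptoglobin. LDH and bilirubin are conditional in Table 4 but are drawn at every dosing visit under the calendar, so they are not lost. The Coombs test depends on suspicion in both tables.

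**Step 4: what happens once hemolysis is suspected?** Appendix C 8.1 has its own diagnostic list, which includes smear, haptoglobin, reticulocyte count, LDH, bilirubin and a direct agglutinin test. That covers the tests that Table 4 leaves optional, conditional or out. The remaining gap is the case in which nobody has yet suspected hemolysis.

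**Step 5: baseline.** Section 3.3.1.9 points to all 11 groups. The calendar fully supplies 3 of them, and Table 4's baseline entry supplies the CBC alone.

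**The case against.** The strongest reply is that a careful investigator reaches the right place. The hemoglobin exception lifts a mandatory stop and does not direct further dosing, so following Appendix C 8.1 breaches nothing in 3.3.1.2. Grade 3 autoimmune hemolysis is treated with prednisone in Appendix C, so it may not count as manageable with transfusion or growth factor at all. Once diagnosed, the event is immune-related, and the NCCN reference may give the correct action. The Appendix C Grade 3 entry is itself not clean: it opens with a permanent stop and later repeats that stop for worsening or no improvement. On work-up, 3.3.1.9 does route evaluation to Table 3. Table 4's CBC is labeled as baseline, and its etiology tests are described as additions to basic testing, so Table 4 can be read as building on Table 3.

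Most of this stands, and it rules out three stronger readings that a reader might infer:

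- *Table 2 restricts the stop to Grade 4.* It does not. It adds a Grade 4 requirement to NCCN and leaves Grade 3 unstated.
- *Section 3.3.1.2 instructs redosing.* It does not. It only removes an obligation to stop.
- *The plan has no adequate work-up for hemolysis.* It has one in Appendix C 8.1, once hemolysis is suspected.

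The reply does not remove the overlap. Whether autoimmune hemolysis falls under the hemoglobin exception is left to interpretation, and the NCCN text that might settle it is not reproduced. Nor does reading Table 4 as an add-on fit its content: it lists bilirubin, LDH and haptoglobin as tests for suspected hemolysis, although Table 3 already makes them basic.

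**Conclusion.** The point holds as a low-severity lack of clarity in safety instructions. At hemoglobin below 8.0 g/dL, section 3.3.1.2 offers an exemption with no clear exclusion for autoimmune hemolytic anemia, Appendix C 8.1 calls for a permanent stop, Table 2 is silent at that grade, and nothing ranks them. Separately, Table 4 duplicates Table 3's work-up in lighter form, which matters only while hemolysis is unsuspected, and the baseline pointer does not match what is scheduled.

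The documents do not give the number of patients affected; it is probably small. ORR, PFS and OS are unchanged. The conclusion assumes that some Grade 3 autoimmune hemolysis could be judged manageable with transfusion, and that an investigator may consult 3.3.1.2 or Table 4 without also opening Appendix C or Table 3.

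**What to change.** 1. Add to the hemoglobin exception in 3.3.1.2: does not apply to autoimmune hemolytic anemia, which is managed per Appendix C 8.1.
2. State in Table 2 that earlier-grade stops in Appendix C still apply, naming Grade 3 for autoimmune hemolytic anemia.
3. Replace Table 4's diagnostic list with a reference to Table 3, and move its suspected aplastic anemia row into Table 3.
4. Change the baseline sentence in 3.3.1.9 to refer to the scheduled CBC with red cell indices (Appendix A).

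The cost is amendment wording. For each suspected treatment-related anemia it also includes the Table 3 tests not on the calendar: reticulocytes, smear, haptoglobin, iron panel, folate and B12, erythropoietin, fecal occult blood and urine culture. Section 3.3.1.9 already routes to these. No baseline tests or visits are added.
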